9.6 PROTOCOL AMENDMENTS

Any protocol amendments will be prepared by the Sponsor. Protocol amendments will be submitted to the IRB/EC and to regulatory authorities in accordance with local regulatory requirements.

Approval must be obtained from the IRB/EC and regulatory authorities (as locally required) before implementation of any changes, except for changes necessary to eliminate an immediate hazard to patients or changes that involve logistical or administrative aspects only (e.g., change in Medical Monitor or contact information).


Appendix 1: Schedule of Activities

	SCR	Treatment Period												FU	EOS	
		V1	V2	V3	V4	V5	V6	V7	V8	V9	V10	V11	V12			
Visit																
Week	D –35 to –1	D1	W1	W2	W4	W6	W8	W10	W12	W14	W16	W20	W24			
			D8	D15	D29	D43	D57	D71	D85	D99	D113	D141	D169			
(Visit window in days)			(± 2)	(± 3)	(± 4)	(± 4)	(± 4)	(± 4)	(± 4)	(± 4)	(± 4)	(± 4)	(± 5)	(± 5)	ET ^a	UV ^b
Office/Phone visit	O	O	O	O or P	O	P	O	P	O	P	O	P	O	O	O	O
Vital signs ⁱ	x	x	x		x		x		x		x		x	x	x	
ECG (12-lead, single)	x						x				x		x	x	x	
Serum pregnancy test ^j	x															x
Urine pregnancy test ^j		x	x		x		x		x		x		x	x	x	
Hepatitis B/C serology	x															
Hepatitis B DNA	x										x			x		
TB test	x															
Chest X-ray, TB worksheet ^k	x															
Hematology ^l	x	x	x		x		x		x		x		x	x	x	
Chemistry ^m	x	x			x		x		x		x		x	x	x	
NT-proBNP		x													x ⁿ	
Urinalysis ^o	x	x									x			x		
HbA ₁ C	x										x		x	x	x	
Fasted glucose and lipids ^p		x									x		x	x	x	
Serum PK ^q		x	x		x		x		x		x		x	x	x	
Serum specific IgE		x														

Appendix 1: Schedule of Activities

	SCR	Treatment Period												FU	EOS	
		V1	V2	V3	V4	V5	V6	V7	V8	V9	V10	V11	V12			
Visit																
Week	D -35	D1	W1	W2	W4	W6	W8	W10	W12	W14	W16	W20	W24			
Day	to -1		D8	D15	D29	D43	D57	D71	D85	D99	D113	D141	D169			
(Visit window in days)			(± 2)	(± 3)	(± 4)	(± 4)	(± 4)	(± 4)	(± 4)	(± 4)	(± 4)	(± 4)	(± 5)	(± 5)	ET ^a	UV ^b
Office/Phone visit	O	O	O	O or P	O	P	O	P	O	P	O	P	O	O	O	O
Serum for biomarker (including total IgE)	x	x	x		x		x				x		x	x		
Serum ADA ^q			x		x						x		x	x		
Randomization			x													
Study drug administration ^s		x	x		x		x		x							
Concomitant medications ^t	x	x	x	x	x	x	x	x	x	x	x	x	x	x	x	x
Adverse events ^u	x	x	x	x	x	x	x	x	x	x	x	x	x	x	x	x

AD=atopic dermatitis; ADA=anti-drug antibody; [REDACTED] D=day; EASI=Eczema Area and Severity Index; eCRF=electronic Case Report Form; EOS=end of study visit; ET=early termination visit; FU=follow up; HbA_{1c}=hemoglobin A_{1c};

IGA=Investigator's Global Assessment; NRS=Numeric Rating Scale; NT-proBNP=N-terminal pro B-type natriuretic peptide; O=office visit; P=phone visit; PK=pharmacokinetic; PPD=purified protein derivative; PRO=patient-reported outcome; QFT=QuantIFERON TB-Gold®;

[REDACTED] SCORAD=SCORing Atopic Dermatitis; SCR=screening; [REDACTED]

TB=tuberculosis; UV=unscheduled visit; V=visit; W=week.

Notes: On treatment days, all assessments should be performed prior to dosing, unless otherwise specified. Visit windows should be calculated relative to the randomization visit (Day 1).

Appendix 1: Schedule of Activities

- ^a If a patient is unable to complete all study visits and assessments, the patient should be asked to return to the clinic for an early termination visit. This visit should occur approximately 4 weeks after the final dose of study drug (see Section 4.6.2).
- ^b Any of the study procedures noted may be performed at an unscheduled visit, but not all are required.
- ^c Informed consent must be documented before any study-specific screening procedure is performed.
- ^d Includes evaluation of the head, eyes, ears, nose, and throat, and the cardiovascular, dermatologic, musculoskeletal, respiratory, gastrointestinal, and neurologic systems. Record abnormalities observed at baseline on the General Medical History and Baseline Conditions eCRF. At subsequent visits, record new or worsened clinically significant abnormalities on the Adverse Event eCRF.
- ^e Perform a limited, symptom-directed examination at specified timepoints and as clinically indicated. Record new or worsened clinically significant abnormalities on the Adverse Event eCRF.
- ^f Questionnaires (██████████, pruritus and sleep NRS) will be self- or interviewer-administered before the patient receives any information on disease status, prior to the performance of non-PRO assessments, and prior to the administration of study treatment.
- ^g Assessment will be conducted only during an office visit (i.e., not at a telephone visit).
- ^h Will only be conducted at a telephone visit. For the Week 2 visit, if the patient does not have an office visit (chooses a telephone visit), collect pruritus and sleep NRS.
- ⁱ Includes respiratory rate, pulse rate, and systolic and diastolic blood pressure, ideally while the patient is in a seated position, and temperature. Record abnormalities observed at baseline on the appropriate eCRF. At subsequent visits, record new or worsened clinically significant abnormalities on the Adverse Event eCRF.
- ^j All women of childbearing potential will have a serum pregnancy test at screening. Urine pregnancy tests will be performed at specified subsequent visits. If a urine pregnancy test result is positive, it must be reported immediately, and study drug will not be administered that day. The positive urine pregnancy result must be confirmed by a serum pregnancy test. Refer to Section 5.4.3.1 for management of a patient with a positive pregnancy test.
- ^k Patients with a positive PPD (without a history of Bacillus Calmette-Guérin vaccination) or a positive or indeterminate QFT will require a chest X-ray to review for evidence of active TB, including posteroanterior and lateral views, unless a chest X-ray has been performed within 3 months before screening and the report is available for review. A chest computed tomography scan may substitute for a chest X-ray. Chest X-rays should only be performed if patients first meet all other study eligibility criteria.
- ^l Hematology includes WBC count, RBC count, hemoglobin, hematocrit, platelet count, and differential count (neutrophils, eosinophils, basophils, monocytes, lymphocytes, other cells).
- ^m Chemistry panel (serum or plasma) includes bicarbonate or total carbon dioxide (if considered standard of care for the region), sodium, potassium, chloride, glucose, BUN or urea, creatinine, total protein, albumin, phosphorus, calcium, total and direct bilirubin, ALP, ALT, AST.

Appendix 1: Schedule of Activities

- As clinically indicated.
- Urinalysis includes dipstick (pH, specific gravity, glucose, protein, ketones, blood) and microscopic examination (sediment, RBCs, WBCs, casts, crystals, epithelial cells, bacteria).
- If patient has not fasted for 8 hours, the patient must return to the site for fasting blood draw only. All other visit assessments should be completed within the regular visit.
- PK and ADA samples to be collected prior to study drug administration.
[REDACTED]
- Patients will receive 490 mg MSTT1041A or placebo at Day 1, Week 4, 8, and 12 visits administered as four SC injections (one in each quadrant of the abdomen). The dose at the Week 1 visit will be 245 mg MSTT1041A or placebo (loading dose) administered as two SC injections (see Section 4.3.2.1 for details).
- Medication (e.g., prescription drugs, over-the-counter drugs, vaccines, herbal or homeopathic remedies, nutritional supplements, emollients) used by a patient in addition to protocol-mandated treatment from 6 months before screening until 12 weeks after the final dose of study drug.
- After informed consent has been obtained but prior to initiation of study drug, only serious adverse events caused by a protocol-mandated intervention should be reported. After initiation of study drug, all adverse events will be reported until 12 weeks after the after the final dose of study drug. After this period, the Sponsor should be notified if the investigator becomes aware of any serious adverse event that is believed to be related to prior study drug treatment (see Section 5.6).

[figure not shown]
Appendix 2

WHO Classification of Topical Corticosteroids

The following table provides a non-exhaustive list of examples of topical corticosteroids classified by potency (Source: <http://apps.who.int/medicinedocs/en/d/Jh2918e/32.html>).

Potency	Class	Topical Corticosteroid	Formulation
Ultra High	I	Clobetasol propionate	Cream, 0.05%
		Diflorasone diacetate	Ointment, 0.05%
High	II	Amcinonide	Ointment, 0.1%
		Betamethasone dipropionate	Ointment, 0.05%
		Desoximetasone	Cream or ointment, 0.025%
		Fluocinonide	Cream, ointment or gel, 0.05%
		Halcinonide	Cream, 0.1%
		Betamethasone dipropionate	Cream, 0.05%
		Betamethasone valerate	Ointment, 0.1%
		Diflorasone diacetate	Cream, 0.05%
		Triamcinolone acetonide	Ointment, 0.1%
		Desoximetasone	Cream, 0.05%
		Fluocinolone acetonide	Ointment, 0.025%
		Fludroxcortide	Ointment, 0.05%
		Hydrocortisone valerate	Ointment, 0.2%
		Triamcinolone acetonide	Cream, 0.1%
		Betamethasone dipropionate	Lotion, 0.02%
		Betamethasone valerate	Cream, 0.1%
		Fluocinolone acetonide	Cream, 0.025%
		Fludroxcortide	Cream, 0.05%
		Hydrocortisone butyrate	Cream, 0.1%
		Hydrocortisone valerate	Cream, 0.2%
		Triamcinolone acetonide	Lotion, 0.1%
		Betamethasone valerate	Lotion, 0.05%
		Desonide	Cream, 0.05%
		Fluocinolone acetonide	Solution, 0.01%
		Dexamethasone sodium phosphate	Cream, 0.1%
		Hydrocortisone acetate	Cream, 1%
		Methylprednisolone acetate	Cream, 0.25%

Appendix 3 Hepatitis B Screening Flowchart

HBcAb = hepatitis B core antibody; HBsAb = hepatitis B surface antibody; HBsAg = hepatitis B surface antigen; HBV DNA = hepatitis B virus DNA.

Appendix 4

Eczema Area and Severity Index

From: Hanifin JM, Thurston M, Omoto M, et al. The eczema area and severity index (EASI): assessment of reliability in atopic dermatitis. *Exp Dermatol* 2001;10 (1):11–8.

Method

Four individual body regions are assessed: head and neck (H&N), upper limbs (UL; includes the external axillae and hands), trunk (includes the internal axillae and groin), and lower limbs (LL; includes the buttocks and feet).

For each body region

- Assess the affected body surface area (BSA): score of 0 to 6 (see Table 1 footnote 3 below) assigned for the percentage of affected BSA (0%–100%)
- Individually rate the average degree of severity (0–3: none, mild, moderate, severe), with half steps allowed, for each of 4 clinical signs: erythema, induration-papulation, excoriations, and lichenification. A summed score of 0 to 12 is assigned to each body region
- Assign a total body region score: sum of the individual clinical signs score (maximum=12) \times affected area score (maximum=6) \times the body-region index (H&N=0.1, UL=0.2, trunk=0.3, LL=0.4)

Total score (0–72)=the sum of total scores for each of the 4 body region scores.

Appendix 5

SCORing Atopic Dermatitis

[figure not shown]
From: European Task Force on Atopic Dermatitis. Severity scoring of atopic dermatitis: the SCORAD Index (consensus report of the European Task Force on Atopic Dermatitis). *Dermatology* 1993;186:23–31.

Three aspects of disease severity are scored

[figure not shown]
- A. Extent (A): A sum of the affected (inflammation, not dryness) body areas as indicated in the figure (Total Score: 0–100)
- B. Intensity (B): Six clinical signs, rated 0–3 for severity (absent, mild, moderate, severe): erythema, edema/papulation, oozing/crusting, excoriation, lichenification, and dryness (Total Score: 0–18)
- C. Subjective (C): Two patient-reported outcomes (PRO) are assessed by numeric rating scale (NRS) scored 0–10 i) Pruritus, ii) Sleep loss (Total PRO Score 0–20)

The NRS is a simple assessment tool that patients will use to report the intensity of their pruritus (itch) and sleep loss during a recall period of 3 days. Patients will be asked the following questions:

For average itch intensity: “On a scale of 0 to 10, with 0 being ‘no itch’ and 10 being the ‘worst itch imaginable,’ how would you rate your itch overall (on average) during the previous 3 days?”

For average sleep loss: “On a scale of 0 to 10, with 0 being ‘no sleep loss’ and 10 being the ‘most severe loss’, how would you rate your sleep loss overall (on average) during the previous 3 days?”

A total score (0–103) is calculated using the following formula: $A/5 + (7B/2) + C$.

Appendix 6 **Investigator Global Assessment**

Score		Description
0	Clear	No erythema. No edema or induration/papulation. No oozing/crusting. Post inflammatory hyper- or hypopigmentation may be present.
1	Almost clear	Trace, faint pink erythema with barely perceptible edema and/or induration/papulation. No oozing/crusting.
2	Mild disease	Faint pink erythema with edema and/or induration and with papulation perceptible upon palpitation. No oozing/crusting.
3	Moderate disease	Pink-red with definite edema and/or induration of skin papules and plaques. There may be some oozing/crusting.
4	Severe disease	Deep/bright red erythema with significant edema and/or induration. Obvious raised borders with papules and plaques with oozing/crusting.

Appendix 8

WHO Toxicity Grading Scale

ITEM	Grade 1 Toxicity	Grade 2 Toxicity	Grade 3 Toxicity	Grade 4 Toxicity
HEMATOLOGY				
Hemoglobin	9.5–10.5 gm/DL	8.0–9.4 gm/DL	6.5–7.9 gm/DL	< 6.5 gm/DL
Absolute neutrophil count	1000–1500/mm ³	750–999/mm ³	500–749/mm ³	<500/mm ³
Platelets	75000–99000/mm ³	50000–74999/mm ³	20000–49000/mm ³	<20000/mm ³
PT	1.01–1.25 × ULN	1.26–1.5 × ULN	1.51–3.0 × ULN	>3 × ULN
aPPT	1.01–1.66 × ULN	1.67–2.33 × ULN	2.34–3 × ULN	>3 × ULN
Fibrinogen	0.75–0.99 × LLN	0.50–0.74 × LLN	0.25–0.49 × LLN	<0.25 × LLN
Fibrin split product	20–40 mcg/ml	41–50 mcg/ml	51–60 mcg/ml	>60 mcg/ml
Methemoglobin	5–9.9 %	10.0–14.9 %	15.0–19.9 %	>20 %
LIVER ENZYMES				
AST (SGOT)	1.25–2.5 × ULN	2.6–5 × ULN	5.1–10 × ULN	>10 × ULN
ALT (SGPT)	1.25–2.5 × ULN	2.6–5 × ULN	5.1–10 × ULN	>10 × ULN
GGT	1.25–2.5 × ULN	1.6–5 × ULN	5.1–10 × ULN	>10 × ULN
ALP	1.25–2.5 × ULN	1.6–5 × ULN	5.1–10 × ULN	>10 × ULN
Amylase	1.1–1.5 × ULN	1.6–2.0 × ULN	2.1–5.0 × ULN	>5.1 × ULN
CHEMISTRIES				
Hyponatremia	130–135 mEq/L	123–129 mEq/L	116–122 mEq/L	<116 or mental status changes or seizures
Hypernatremia	146–150 mEq/L	151–157 mEq/L	158–165 mEq/L	>165 mEq/L or mental status changes or seizures
Hypokalemia	3.0–3.4 mEq/L	2.5–2.9 mEq/L	2.0–2.4 mEq/L or intensive replacement Rx required or hospitalization required.	<2.0 mEq/L or paresis or ileus or life-threatening arrhythmia
Hyperkalemia	5.6–6.0 mEq/L	6.1–6.5 mEq/L	6.6–7.0 mEq/L	>7.0 mEq/L or life-threatening arrhythmia
Hypoglycemia	55–64 mg/dL	40–54 mg/dL	30–39 mg/dL	<30 mg/dL or mental status changes or coma
Hyperglycemia (note if fasting)	116–160 mg/dL	161–250 mg/dL	251–500 mg/dL	>500 mg/dL or ketoacidosis or seizures

Appendix 8: WHO Toxicity Grading Scale

ITEM	Grade 1 Toxicity	Grade 2 Toxicity	Grade 3 Toxicity	Grade 4 Toxicity
Hypocalcemia (corrected for albumin)	8.4–7.8 mg/dL	7.7–7.0 mg/dL	6.9–6.1 mg/dL	< 6.1 mg/dL or life-threatening arrhythmia or tetany
Hypercalcemia (correct for albumin)	10.6–11.5 mg/dL	11.6–12.5 mg/dL	12.6–13.5 mg/dL	> 13.5 mg/dL life-threatening arrhythmia
Hypomagnesemia	1.4–1.2 mEq/L	1.1–0.9 mEq/L	0.8–0.6 mEq/L	< 0.6 mEq/L or life-threatening arrhythmia
Hypophosphatemia	2.0–2.4 mg/dL	1.5–1.9 mg/dL or replacement Rx required	1.0–1.4 mg/dL intensive Rx or hospitalization required	< 1.0 mg/dL or life-threatening arrhythmia
Hyperbilirubinemia	1.1–1.5 × ULN	1.6–2.5 × ULN	2.6–5 × ULN	> 5 × ULN
BUN	1.25–2.5 × ULN	2.6–5 × ULN	5.1–10 × ULN	> 10 × ULN
Creatinine	1.1 × 1.5 × ULN	1.6–3.0 × ULN	3.1–6 × ULN	> 6 × ULN or required dialysis
URINALYSIS				
Proteinuria	1+ or < 0.3% or < 3 g/L or 200 mg–1 gm loss/day	2–3+ or 0.3%–1.0% or 3–10 g/L or 1–2 gm loss/day	4+ or > 1.0% or > 10 g/L or 2–3.5 gm loss/day	nephrotic syndrome or > 3.5 gm loss/day
Hematuria	Microscopic only	Gross, no clots	Gross+ clots	Obstructive or required transfusion
CARDIAC DYSFUNCTION				
Cardiac rhythm		Asymptomatic, transient signs, no Rx required	Recurrent/persistent; No Rx required	Requires treatment
Hypertension	Transient inc. > 20 mm; no Rx	Recurrent, chronic, > 20 mm, Rx required	Requires acute Rx; no hospitalization	Requires hospitalization
Hypotension	Transient orthostatic hypotension, no Rx	Symptoms correctable with oral fluids Rx	Requires IV fluids; no hospitalization required	Requires hospitalization
Pericarditis	Minimal effusion	Mild/moderate asymptomatic effusion, no Rx	Symptomatic effusion; pain; EKG changes	Tamponade; pericardiocentesis or surgery required

Appendix 8: WHO Toxicity Grading Scale

ITEM	Grade 1 Toxicity	Grade 2 Toxicity	Grade 3 Toxicity	Grade 4 Toxicity
Hemorrhage, blood loss	Microscopic/occult	Mild, no transfusion	Gross blood loss; 1–2 units transfused	Massive blood loss; > 3 units transfused
RESPIRATORY				
Cough	Transient-no Rx	Treatment associated cough; local Rx	Uncontrolled	
Bronchospasm, acute	Transient; no Rx < 80%–70% FEV ₁ (or peak flow)	Requires Rx normalizes with bronchodilator; FEV ₁ 50%–70% (or peak Flow)	No normalization with bronchodilator; FEV ₁ 25%–50% (or peak flow retractions)	Cyanosis: FEV ₁ < 25% (or peak flow) or Intubated
GASTROINTESTINAL				
Stomatitis	Mild discomfort; no limits on activity	Some limits on eating/drinking	Eating/talking very limited	Requires IV fluids
Nausea	Mild discomfort; maintains reasonable intake	Moderate discomfort; intake decreased significantly; some activity limited	Severe discomfort; no significant intake; activities limited	Minimal fluid intake
Vomiting	Transient emesis	Occasional/moderate vomiting	Orthostatic hypotension or IV fluids required	Hypotensive shock or hospitalization required for IV fluid therapy
Constipation	Mild	Moderate	Severe	Distensions w/ vomiting
Diarrhea	Transient 3–4 loose stools/day	5–7 loose stools/day	Orthostatic hypotension or > 7 loose stools/day or required IV fluids	Hypotensive shock or hospitalization for IV fluid therapy required
NEURO & NEUROMUSCULAR				
Neuro-cerebellar	Slight incoordination dysdiadochokinesis	Intention tremor, dysmetria, slurred speech; nystagmus	Locomotor ataxia	Incapacitated
Mood	Mild anxiety or depression	Moderate anxiety or depression and therapy required	Severe anxiety or depression or mania; needs assistance	Acute psychosis; incapacitated, requires hospitalization

Appendix 8: WHO Toxicity Grading Scale

ITEM	Grade 1 Toxicity	Grade 2 Toxicity	Grade 3 Toxicity	Grade 4 Toxicity
Neuro control	Mild difficulty concentrating; no Rx; mild confusion/agitation; ADL unaffected	Moderate confusion/agitation some limitation of ADL; minimal Rx	Severe confusion/agitation needs assistance for ADL; therapy required	Toxic psychosis; hospitalization
Muscle strength	Subjective weakness; no objective symptoms/signs	Mild objective signs/symptoms; no decrease in function	Objective weakness function limited	Paralysis
OTHER PARAMETERS				
Fever: oral, > 12 hours	37.7–38.5°C or 100.0–101.5°F	38.6–39.5°C or 101.6–102.9°F	39.6–40.5°C or 103–105°F	> 40 C or > 105°F
Headache	Mild, no Rx therapy	Transient, moderate; Rx required	Severe; responds to initial narcotic therapy	Intractable; required repeated narcotic therapy
Fatigue	No decrease in ADL	Normal activity decreased 25%–50%	Normal activity decreased > 50% can't work	Unable to care for self
Allergic reaction	Pruritus without rash	Localized urticaria	Generalized urticaria; angioedema	Anaphylaxis
Local reaction	Tenderness or erythema	Induration < 10 cm or phlebitis or inflammation	Induration > 10 cm or ulceration	Necrosis
Mucocutaneous	Erythema; pruritus	Diffuse, maculo-papular rash, dry desquamation	Vesiculation, moist desquamation, or ulceration	Exfoliative dermatitis, mucous membrane involvement or erythema, multiforme or suspected Stevens-Johnson or necrosis requiring surgery

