2.2 SAFETY OBJECTIVE

The safety objective for this study is to evaluate the safety of MSTT1041A compared with placebo on the basis of the following endpoints:

- Incidence and severity of adverse events, with severity determined according to the WHO toxicity scale
- Change from randomization visit in vital signs, ECGs, and clinical laboratory results

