- Patient is not eligible, if HBV DNA test value is ≥ 20 IU/mL or test cannot be performed.
- Patient is eligible, if HBV DNA test value is < 20 IU/mL.
- Evidence of active liver disease, including jaundice or AST, ALT, total bilirubin, or ALP $> 2 \times$ upper limit of normal (ULN) at screening

- History of anaphylaxis, hypersensitivity to a biologic agent, or known hypersensitivity to any component of the MSTT1041A or placebo injection
- Neutrophil count $\leq 0.5 \times 10^3/\mu\text{L}$ at screening
- Platelet count $\leq 50 \times 10^3/\mu\text{L}$ at screening
- Presence of skin comorbidities that may interfere with study assessments, in the opinion of the investigator
- Active malignancy, including cutaneous basal or squamous cell carcinoma or melanoma
- History of malignancy within 5 years before screening, except for cases of cervical carcinoma in situ or breast ductal carcinoma in situ that have been treated and considered cured
- Helminthic parasitic infection diagnosed within 6 months before screening that has not been treated or has not responded to standard-of-care therapy or exposure to water-born parasites within 6 weeks before screening
- History or evidence of substance abuse that would pose a risk to patient safety, interfere with the conduct of the study, have an impact on the study results, or affect the patient's ability to participate in the study, in the opinion of the investigator
- Hemoglobin A1c (HbA_{1c}) $> 8.5\%$ at screening or any other clinically significant finding that, in the opinion of the investigator, may define uncontrolled diabetes
- History of myocardial infarction, congestive heart failure NYHA Class III and IV, unstable angina pectoris, or stroke within 12 months before screening
- History or presence of complete left bundle branch block, second- or third-degree atrioventricular heart block, or evidence of prior myocardial infarction on ECG, or any abnormality that is clinically significant in the investigator's opinion
- QT interval corrected through use of Fridericia's formula (QTcF) > 450 ms, if patient is male, or QTcF > 470 ms, if patient is female

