4.5.6 Laboratory, Biomarker, and Other Biological Samples

Samples for the following laboratory tests will be sent to the study site's local laboratory for analysis or analyzed at point of care:

- Urine pregnancy test for all women of childbearing potential

Urine pregnancy tests will be performed at the site prior to each administration of study drug and at other specified visits after treatment discontinuation. If a local urine pregnancy test result is positive, it must be reported immediately, and study drug will not be administered that day. The positive urine pregnancy result must be confirmed by a serum pregnancy test (conducted by the central laboratory). Refer to Section 5.4.3.1 for management of a patient with a positive pregnancy test.
- TB tests: PPD or QFT (QFT may be conducted by the central laboratory, per Sponsor agreement with site)

Samples for the following laboratory tests will be sent to one or several central laboratories for analysis:

- Hematology: WBC count, RBC count, hemoglobin, hematocrit, platelet count, and differential count (neutrophils, eosinophils, basophils, monocytes, lymphocytes, other cells)
- Chemistry panel (serum or plasma): bicarbonate or total carbon dioxide (if considered standard of care for the region), sodium, potassium, chloride, glucose, BUN or urea, creatinine, total protein, albumin, phosphorus, calcium, total and direct bilirubin, ALP, ALT, AST
- Fasting lipids: total cholesterol, LDL cholesterol, HDL cholesterol, triglycerides
- Fasting glucose
- HbA_{1c}
- N-terminal pro B-type natriuretic peptide
- Serum pregnancy test
- Urinalysis, including dipstick (pH, specific gravity, glucose, protein, ketones, blood) and microscopic examination (sediment, RBCs, WBCs, casts, crystals, epithelial cells, bacteria)

- Viral serology: HBsAb, HBsAg, HBCAb, HCV antibody
 - If HBsAb testing is positive and HBCAb is positive, patient must undergo further testing for HBV DNA.

Blood samples will be collected to evaluate the pharmacokinetics of MSTT1041A in serum as noted in the schedule of activities (see [Appendix 1](#)). Serum concentrations of MSTT1041A will be determined using validated analytical procedures.

The following samples will be sent to the Sponsor or a designee for analysis:

- Serum samples for MSTT1041A PK analysis
- Serum samples for immunogenicity analysis
- Serum samples for specific IgE, and total IgE, and other biomarkers; mandatory blood

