5.3.3 Assessment of Severity of Adverse Events

The WHO toxicity grading scale (see [Appendix 8](#)) will be used for assessing adverse event severity. [Table 2](#) will be used for assessing severity for adverse events that are not specifically listed in the WHO toxicity grading scale.

Table 2 Adverse Event Severity Grading Scale for Events Not Specifically Listed in WHO Toxicity Grading Scale

Grade	Severity
1	Mild; transient or mild discomfort (<48 hours); no medical intervention or therapy required
2	Moderate; mild to moderate limitation in activity; some assistance may be needed; no or minimal medical intervention or therapy required
3	Severe; marked limitation in activity; some assistance usually required; medical intervention or therapy required; hospitalization possible
4	Life-threatening; extreme limitation in activity; significant assistance required; significant medical intervention or therapy required, hospitalization or hospice care probable

Notes: Developed by the Division of Microbiology and Infectious Diseases.

Regardless of severity, some events may also meet seriousness criteria. Refer to definition of a serious adverse event (see Section [5.2.2](#)).

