6.5 SAFETY ANALYSES

The safety analysis population will consist of all randomized patients who received at least one dose of study drug, with patients grouped according to actual treatment received.

Safety will be assessed by adverse events, clinical laboratory evaluations, vital signs, and ECGs. All verbatim adverse event terms will be mapped to MedDRA thesaurus terms, and adverse event severity will be graded according to the WHO toxicity grading. The incidence of mapped adverse events will be summarized by treatment arm.

A treatment emergent adverse event is defined as any new adverse event reported or any worsening of an existing condition on or after the first dose of study drug. Treatment emergent adverse event will be summarized by treatment arm. Clinical laboratory data (hematology and serum chemistry), vital signs, and ECGs will be summarized by descriptive statistics by treatment groups at each visit. In addition, separate summaries will be generated for serious adverse events, adverse events of special interest, deaths, pregnancies, malignancies, adverse events leading to discontinuation from the study, and adverse events leading to discontinuation of study drug.

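### Appendix 8 assigns two grades to the same value for part of the fever and ALP ranges, and the plan has no tie rule (minor)

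*Combined protocol and SAP*

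**What the plan says.** Section 2.2 gives as the first safety endpoint "Incidence and severity of adverse events, with severity determined according to the WHO toxicity scale". Section 5.3.3 says that the scale in Appendix 8 "will be used for assessing adverse event severity", and that Table 2 "will be used for assessing severity for adverse events that are not specifically listed in the WHO toxicity grading scale". Section 6.5 repeats for the analysis that "adverse event severity will be graded according to the WHO toxicity grading".

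In Appendix 8 the Grade 3 fever cell reads "39.6–40.5°C or 103–105°F". The relevant rows are:

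| Row | Grade 1 | Grade 2 | Grade 3 | Grade 4 |
|---|---|---|---|---|
| Fever (oral, lasting more than 12 hours), °C | 37.7–38.5 | 38.6–39.5 | 39.6–40.5 | > 40 |
| Fever, °F | 100.0–101.5 | 101.6–102.9 | 103–105 | > 105 |
| ALP and GGT, × ULN | 1.25–2.5 | 1.6–5 | 5.1–10 | > 10 |
| AST and ALT, × ULN (for comparison) | 1.25–2.5 | 2.6–5 | 5.1–10 | > 10 |

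Temperature is one of the vital signs in Section 4.5.5, which states no unit. The central chemistry panel in Section 4.5.6 ends with "total and direct bilirubin, ALP, ALT, AST"; GGT is not listed there. Section 4.1.2 excludes patients only when ALP is above 2 × ULN at screening.

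**The concern.** A grading scale has to put each value in one grade. Here, parts of two rows that apply to this trial put a value in two. The scale is the operative definition of severity in Sections 2.2, 5.3.3 and 6.5, so the flaw lies in the endpoint definition itself.

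Two consequences follow from the text. First, sites can grade the same event differently with neither departing from the protocol. For fever the choice is between Grade 3 and Grade 4, and Table 2 labels its own Grade 4 as life-threatening. Second, Section 5.5.1 has the investigator follow an adverse event until it returns to the baseline grade or better (or another listed stopping point is reached). For a patient enrolled with ALP of 1.6–2.0 × ULN, the baseline grade is both 1 and 2.

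**Working it through.** The plan states no figure to reproduce. The check compares the upper limit of each grade with the lower limit of the next, and converts temperatures with °F = 9 × °C / 5 + 32.

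**1. Fever, Celsius.** Grade 3 ends at 40.5 and Grade 4 starts above 40. Overlap: 40.5 − 40.0 = 0.5°C. The Grade 3 band is 40.5 − 39.6 = 0.9°C wide, so the overlap is 0.5 / 0.9 = 56% of it.

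**2. Fever, Fahrenheit.** Grade 3 ends at 105 and Grade 4 starts above 105. There is no overlap.

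**3. Units against each other.**
- 40.0°C = 9 × 40.0 / 5 + 32 = 104.0°F
- 40.5°C = 9 × 40.5 / 5 + 32 = 104.9°F
- 105°F = (105 − 32) × 5 / 9 = 40.56°C

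The two Grade 4 limits are 40.56 − 40.00 = 0.56°C apart. As an example, 104.5°F is (104.5 − 32) × 5 / 9 = 40.3°C: Grade 3 only on the Fahrenheit limits, and Grades 3 and 4 on the Celsius limits. A smaller mismatch sits at the Grade 2/3 boundary: 39.5°C is Grade 2 in Celsius, but it converts to 103.1°F, which is Grade 3 in Fahrenheit.

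**4. ALP (and GGT).** Grade 1 ends at 2.5 × ULN and Grade 2 starts at 1.6 × ULN. Overlap: 2.5 − 1.6 = 0.9. The Grade 1 band is 2.5 − 1.25 = 1.25 wide, so the overlap is 0.9 / 1.25 = 72% of it.

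The 56% and 72% are shares of interval width, not of patients or events.

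**5. Comparison rows.** The same check on AST, ALT, amylase, bilirubin, BUN and creatinine finds no overlap. Overlapping grades are therefore not a convention of the scale.

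**6. Search for a tie rule.** Table 2 does not apply, because fever and ALP are listed in the scale. Section 5.3.5.5 asks for the most extreme severity, but for a persistent event that worsens over time, not for one value that fits two grades. No other section addresses the matter.

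**7. Baseline grade.** ALP of 1.6–2.0 × ULN passes the exclusion limit and lies in the overlap. Suppose such a patient later has an ALP adverse event with values above 2.5 and up to 5 × ULN, which is Grade 2 only. If baseline is read as Grade 2, the event is already at baseline grade; if baseline is read as Grade 1, it is not. The follow-up rule gives two answers.

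**8. Size in the tables.** About 90 / 2 = 45 patients per arm. One re-graded patient changes an arm's incidence of that grade by 1 / 45 = 2.2 percentage points. The documents give no expected count. If 0 to 3 patients are affected, and all three fall in one arm at worst, the range is 0 to 3 / 45 = 6.7 points.

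**The case against.** The case for leaving this alone is that it will hardly ever matter, and most of that case stands.

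- The fever row requires an oral temperature lasting more than 12 hours. Few adults in a trial of 90 are likely to hold a temperature above 40.0 and up to 40.5°C for that long.
- Under Section 5.3.5.6, an ALP value becomes an adverse event only if it is symptomatic, changes study treatment, leads to an intervention or a change in concomitant therapy, or is judged clinically significant. If it is a sign of a disease, only the diagnosis is recorded. Under Section 5.3.5.10, a condition present at screening counts only if it worsens.
- No stated action turns on these grades. Table 1 uses direct multiples of ULN, and its ALP threshold of 3 × ULN lies above the disputed window. Immediate reporting follows seriousness, which Section 5.2.2 separates from severity, or special-interest status. Section 5.7 has the sponsor compare severity with the Investigator's Brochure, but sets no rule in terms of Appendix 8 grades.
- The Grade 4 fever cell lacks the degree sign used elsewhere in its row, so a lost character cannot be excluded. Nothing shows one, and it would not explain ALP and GGT.

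These points limit the consequence. They do not remove the overlap or supply a tie rule.

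A reader might infer more than the documents support:
- *That grading will differ by region.* No section says which temperature unit a site, a region or the eCRF uses. The Celsius overlap exists whatever the unit.
- *That an analysis of grade shift from baseline is undefined.* Section 6.5 plans descriptive statistics of laboratory values by visit and no grade-shift table. Baseline grade enters only through the follow-up rule in Section 5.5.1.
- *That a prominent Grade 4 row of the safety report will be wrong.* Section 6.5 specifies no separate Grade 4 summary.
- *That the ALP Grade 2 lower limit is the misprint.* The AST and ALT rows suggest this. But amylase and bilirubin end Grade 1 at 1.5 × ULN and start Grade 2 at 1.6, so the Grade 1 upper limit could equally be at fault.

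**Conclusion.** The inconsistency is real and is in the current text. Part of the fever row and part of the ALP row of the scale that defines the severity endpoint give two grades to one value, and the fever limits disagree between units. This is a minor point. It applies only to qualifying fevers above 40.0 and up to 40.5°C, plus the narrow unit mismatch near 39.5°C, and to ALP of 1.6–2.5 × ULN that has become a reportable adverse event. The GGT overlap has little practical effect, because GGT is not in the listed panel. The plausible damage is a few differently graded events in the safety tables, at 2.2 points per patient in an arm of about 45, and an unclear follow-up endpoint for an ALP event in a patient enrolled at 1.6–2.0 × ULN. Efficacy is untouched. The count of 0 to 3 patients is an assumption. The overlaps and conversions rest only on the printed limits.

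**What to change.** Check the fever, ALP and GGT rows of Appendix 8 against the source scale and correct them so that each value falls in exactly one grade and the °C and °F limits agree at every boundary. Failing that, state in Section 5.3.3 one rule for a value that meets two grades, to be applied by all sites and to the baseline grade in Section 5.5.1. The sponsor decides which limits are right; the documents do not settle it.

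Deriving these grades centrally from recorded values would not be a full substitute. Section 5.3 makes severity the investigator's assessment, and a single temperature cannot show that a fever lasted more than 12 hours.

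The cost is three table rows or one sentence, with no new data. Because it changes the protocol text, it goes through the amendment process in Section 9.6 and could be carried with the next amendment.
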